This is a collaborative clinical study that involves various components being administered from one of 3 sites: East Orange VA, Bedford VA, and Canandaigua VA. Recruitment will occur from all three sites. In addition, Veterans will consent and complete the baseline assessment and 12th session assessment in-person at one of the three sites. East Orange VA will provide the PST or health education via phone to all participants in the study. As needed, all sites, including East Orange VA, Bedford VA and Canandaigua VA, will assist with all parts of the study.

Data from all sites (East Orange VA, Canandaigua VA, and Bedford VA) will be kept on a VANJHCS server in a shared network folder created by IRM in East Orange, NJ. All data and study materials, including PHI from screening and recruitment, questionnaire data, neuropsychological data, and qualitative recordings and transcriptions will be stored and shared by all three sites via the shared network folder. This folder will have restricted access to study personnel approved on the protocol. Data will be collected in accordance with the protocol and under supervision of qualified personnel. Data may also be placed on the VA VINCI platform for data analysis.

There exists the possible risk of loss of confidentiality. We minimize these risks by assigning participants a unique study ID that is coded and which we will use on all electronic files resulting from their participation. The "link" or key that matches the ID code with participants' personal information will be kept in an electronic study folder on the server administered by IRM in East Orange in the IRM server room with access granted only to the PI and study staff across study sites.

In addition, all other paper documents, including signed consent forms, forms that ask for contact information, hard copies of data, and completed questionnaires, will be kept in a locked cabinet in room 11-198.

All recorded data from the therapy sessions and qualitative interviews will be stored on the network shared folder on the secure VA server with access limited to the research team. Before

being uploaded to the server, audio recorders will be stored in a locked cabinet with access to only study team members. The recordings may then be transcribed, with transcriptions stored on the same limited-access server. Transcriptions will generally contain no identifying information; basic information on gender and age range will be attached to each subject in the transcript, who will be identified with the assigned unique ID number (e.g., 10012).

The PI and study team members only will have access to the data and no confidential data will be shared with individuals outside of this team. Once a member of the study team leaves the study, s/he will no longer have access to any of the data or study folders.

Data use agreements and proper approvals will be put into place with collaborators from outside institutions for data analyses.

Incident Reporting:

In the case that any digital recorders, electronic data, or hard copies of any research files and study data are compromised (e.g., lost, theft, unauthorized access, non-compliance with security controls), the PI will report the incident to the appropriate authorities/committees, including the VA NJHCS Information Security Officer and Privacy Officer within 1 hour of discovery, and will assist in the investigation and/or remediation of the incident.

Plan for destruction/return of data:

Study records will be destroyed in accordance with VHA RCS 10-1, and no less than 6 years past the date of study closure. All study records that are kept at the VA, including the links, will be destroyed in accordance with VHA RCS 10-1 and no less than 6 years past the date of study closure.

Data Analysis

a. Data

Data analyses will be conducted both on-site by study investigators and with proper approvals, including DUAs, at our affiliate institutes by current and future study investigators. All analyses will be primarily performed on an intention-to-treat basis. The statistical significance will be defined by a p value < 0.05 , unless specified otherwise. Calculations of the means, standard deviations, proportions, histograms, etc., will be conducted to explore the distributions of the data, identify outliers, and calculate correlations between variables. We will also determine confounders that need to be controlled for in our analyses. We will particularly examine if we need to control for depression measured with the PHQ-8 or PTSD symptoms measured with the PCL based characteristics that exhibit differences at the baseline (pre-intervention).

Due to repeated measures, we will analyze the data using mixed model analysis, with participants nested within therapists modeled by random effects. To address H1, disability (WHODAS II scores) will be treated as the dependent variable, and treatment assignment [PST vs. Health education], time [pre- vs. post-intervention] and their interaction will be modeled as fixed effects. Differences in the improvement of disability between Problem-solving therapy and Health education will be evaluated by the treatment by time interaction. Linear contrasts will be constructed to evaluate the improvement in disability for each treatment separately. Variables such as age, gender, education and the confounders identified in the preliminary analysis will be controlled as covariates in the statistical analyses. Data transformations (e.g., square root, log,

etc.) will be used to normalize data where necessary. The same mixed model analysis strategy will be applied to address H2a, H2b, H3a and H3b. We will also explore, using this same mixed model strategy, the impact of PST therapy on each of the four individual neuropsychological tests scored as a composite and scored individually (Category Test, CPT 3, Stroop Test, and TMT). We will use the same data analysis strategy to examine all secondary outcomes. These will be reported as secondary outcomes and will primarily be used to generate hypotheses.

To address the H2c and H2d, we will establish a mediational model to explore whether the PST produces greater improvement in disability through its effects on problem-solving ability (measured by either the self-report (H2c) or the objective measurements (H2d)), following the recommendations of Baron and Kenny. The same mediational model will be used to explore whether participants views of treatment (e.g., relationship with therapist) also mediates the relationship between PST and disability. The statistical analysis will be performed using the mixed model analysis. Using these general methods we will also examine the impact of the treatment on other outcomes of interest, the relationship between variables and other potential moderators and mediators; we will also explore the relationship between variables of interest assessed concurrently.

b. Qualitative Data

Qualitative interviews will be transcribed and analyzed using standard qualitative research methods. The data to be analyzed are the participants' own words and narratives. Several members of the study team will perform an initial independent read through of interview notes and transcripts and generate a list of domains to create the initial coding scheme. Initial domains are expected to parallel the major themes or questions in the discussion and interview guides. Initial codes will be used to inform ongoing interviews and coding schemes. Once codes have been finalized, the coding scheme, interview notes and transcripts for interviews will be entered into an Excel or a qualitative software package. Study team members will apply the codes and labels to text.

Risks and Benefits

Risks

The risks of this study include:

1. Loss of confidentiality
2. Emotional distress. Some Veterans could find some of the questionnaires and the phone sessions upsetting.
3. As part of the study, Veterans will be encouraged to increase activities of their choosing. Examples of activities may include hobbies, household chores, social activities, or physical activity. Since the activities are personalized, the exact risks are not known. Participants are encouraged to talk with their primary care providers before engaging in activities. Study Providers will use clinical judgment to reduce risks as appropriate. Increasing activity (behavioral activation) is a standard component of cognitive and behavioral treatments. Veterans in the Health education component will be provided with didactic health information. All Veterans will be encouraged to talk with their PCPs prior to implementing any changes.

Benefits

This study will enable us to learn more about treatments that may help individuals with GWI. Some participants may experience improvement in the disability associated with GWI.

Reference List

- Geisser, M. E., Clauw, D. J., Strand, V., Gendreau, R. M., Palmer, R., & Williams, D. A. (2010). Contributions of change in clinical status parameters to Patient Global Impression of Change (PGIC) scores among persons with fibromyalgia treated with milnacipran. *Pain*, 149, 373-378.
- Hays, R. D., Sherbourne, C. D., & Mazel, R. (1995). *User's Manual for the Medical Outcomes Study (MOS) Core Measures of Health-Related Quality of Life*. Santa Monica, CA: RAND.
- Kerns, R. D., Turk, D. C., & Rudy, T. E. (1985). The West Haven-Yale Multidimensional Pain Inventory (WHYMPI). *Pain*, 23, 345-356.
- Moss-Morris, R., Weinman, Petrie, & Horne (2002). The Revised Illness Perception QQuestionnaire (IPQ-R). *Psychology and Health*, 17.

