Once potential participants are identified, introduction letters will be mailed to their addresses. Approximately after two weeks of mailing the introduction letter to Veterans, research staff will contact potential participants to inform them about the study, obtain verbal consent for and conduct initial screenings over the phone. For Veterans who contact us over the phone or in-person, (e.g., after reading a posted flyer), we will obtain verbal consent for and conduct initial screenings in person or over the phone.

If a Veteran is screened as eligible to participate in the study, a date and time will be scheduled for the Veteran to come into one of the three study sites (East Orange VA, Canandaigua VA or Bedford VA) to be consented into the study and complete the baseline questionnaires and neuropsychological assessments.

b. Sessions

Once consented and baseline assessments (described below) are completed, therapy sessions will be scheduled with a Study Provider from the East Orange VA. Study providers will be a licensed provider, e.g., psychologist, nurse, social worker, or a trainee e.g., working under a licensed provider, at the East Orange VA. A Study Provider from the East Orange VA will provide the sessions via phone with all participants from all VA sites (East Orange VA, Canandaigua VA, and Bedford VA). We will have a standardized assessment regimen that all Study Providers will adhere to. Therapy sessions will be scheduled weekly, and may be adjusted to accommodate the Veteran's schedule and/or needs.

The telephone sessions with the Study Provider will generally be 1 hour. Most telephone sessions will be voice recorded and transcribed for quality assurance, i.e., fidelity to study protocols, length of sessions, engagement of participants. Coding of telephone sessions will occur by our off site collaborators once proper approvals are in place (i.e., DUA).

Study Arms

Veterans will be randomized either to the PST (treatment) or Health Education group (control).

If randomized to the PST (treatment):

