A state of the art evidence-based 12 session PST intervention with a structured five step sequential approach to teaching problem-solving will be used. Our goal is to reduce disability (i.e., limitations in daily activities and participation). Study Providers will first work with participants to increase participation in the activities of their choosing. This could include increasing social activities, hobbies, physical activities, etc. Participants are then taught problem-solving skills and encouraged to problem-solve to overcome the barriers with increasing activity.

A 5-step problem-solving approach is employed whereby, 1) the problem is defined and goals are created, 2) possible solutions are generated, 3) these possible solutions are evaluated and one is selected, 4) the chosen solution is implemented in a step-by-step approach, and finally, 5) the outcome of the implemented solution is measured for success. Participants are introduced to the steps incrementally and each is reinforced by working with the Study Provider.

Participants will be given or mailed a PST workbook after the baseline assessment. For participants enrolled at the Bedford VA and Canandaigua VA, the Study Coordinator from the East Orange VA may mail the PST workbook. The content in the PST workbook will help guide participants through each session. The workbook also includes worksheets that are completed during each session and during the participant's own time. The workbooks will then be reviewed with the Study Provider during each session. At the Study Provider's or PI's discretion, the treatment or protocol may vary in order to meet a Veteran's needs (e.g., changing the order of the information given, having an additional session if feasible). During the sessions, participants will regularly be asked questions about their perception of the sessions, treatment, and if they have any new health concerns.

If randomized to the Health Education group (control):

Every week participants will receive up to an hour of didactic information and discussion about a variety of health concerns. Sessions will be highly structured and will emphasize the learning and analysis of key concepts in the presentations. This intervention will also be delivered over the telephone.

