Participants will be given or mailed a Health Education workbook after the baseline assessment. For participants enrolled at the Bedford VA and Canandaigua VA, the Study Coordinator from the East Orange VA may mail the Health Education workbook. The Health Education workbook will be used in conjunction with the sessions. The content in the Health Education workbook includes didactic information on a variety of health topics pertinent to GWVs, i.e., pain, improving cognition, sleep, diet and physical activity. This information will also be reviewed with the Study Provider during each session. Similar to those randomized to the PST group, at the Study Provider's or PI's discretion, the Health Education protocol may vary in order to meet a Veteran's needs (e.g., changing the order of the information given, having an additional session if feasible).

Participants who are assigned to the health education control condition may be offered the 12-session PST program at the end of the study.

During the sessions, participants will regularly be asked questions on their perception of the sessions, treatment and if they have any new health concerns.

Reducing Attrition

To reduce attrition and the burden on the Veteran, all therapy sessions are done over the phone or video to phone if available. In addition, we plan to make phone calls to remind participants about their scheduled appointments (similar to the VA's automated appointment reminder system). PST has been successfully implemented over the telephone. Prior to starting the treatment, the participant and Study Provider may determine the time that is best for the Veteran (including nights and weekends) and may determine ground rules (for example, not having anyone else in the room, shutting off other telephones to remove distractions). The Study Provider and Veteran may also establish verbal signals to substitute for non-verbal cues, for example, "that's great" or "can I interrupt."

Participants will be allowed to begin or continue with their existing medical regimen throughout the course of the trial and make changes to their existing treatments. Adherence to medical protocols and participation in alternate treatments will be evaluated by a questionnaire at the assessments and this will be controlled for in analyses. The Study Provider may make additional recommendations for additional health care if needed or as appropriate.

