We will make a concerted effort to contact participants for their appointments and assessments through phone calls and letters. We will not reach out to Veterans who do not wish to continue in the study.

Consent Procedures

Informed consent is an ongoing process. At the phone screening, Veterans will provide a verbal consent. At the baseline assessment, when the Veteran is considering enrolling in the study, information will be presented in-person to enable the Veteran to voluntarily decide whether or not to participate as a research participant. The Investigator, study coordinator or research assistant will review and explain the study's purpose, experimental procedures, alternatives, risks, benefits and duration of the study in terms that the potential participant can understand. The Investigator or study team member will be available to address any concerns and answer any questions the Veteran might have regarding the study and the informed consent. After all questions have been answered and concerns addressed, the Veteran may sign the Consent Form. A signed copy will be provided to the Veteran and the original copy will be placed in the Veteran's study folder and scanned into his/her CPRS record.

Participant Compensation

Participants may receive a total of \$200 for their participation in the study as follows: \$30 for completion of the baseline assessments; \$70 for completion of the 12th session questionnaires and neuropsychological assessments. We will contact participants after the 4th session and also at 6 months post-treatment to complete written questionnaires – participants will receive \$50 for completing each of these questionnaires. For compensation, participants will complete and sign a voucher, and a check will be mailed within 6-8 weeks. If the subject does not want to continue

in the study, s/he may come to an assessment site and complete a study exit visit and assessment; they will still receive \$70.

Our budget includes funds to pay for participant travel as needed.

c. Assessment Methods

In this section we summarize all of the assessment instruments/procedures used to determine eligibility, assess neuropsychological functioning, and disability.

Table 2 outlines the study procedures that are described below: assessments, mailed questionnaires, qualitative interviews, and therapy sessions with the study provider.

		Weeks												Months
	Baseline	1	2	3	4	5	6	7	8	9	10	11	12	6
Questionnaires	X				X								X	X

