Qualitative assessments and interviews may be recorded, transcribed, and coded for further data analyses. Personal identifiers will not generally be transcribed from the voice recordings.

Additionally, we will review participants' medical records and collect information on previous and future medical treatment including physical and mental health treatment, diagnoses and medication.

c. Neuropsychological Measures

These measures capture Problem-solving Ability or Executive Function. These measures will be administered in-person at the baseline assessment visit and after the 12th session assessment visit. Problem-solving, an executive function refers to the ability of an individual experiencing an undesirable situation to move to a more desirable one when no response is immediately apparent or available. Problem-solving is considered the most complex of all cognitive functions as it requires the use and integration of other cognitive functions like attention, processing speed, effort, and impulse control as well as other executive functioning skills like mental flexibility and abstract thinking. Neuropsychological testing can be used to measure participants' functioning in the entire range of cognitive skills that problem-solving demands. We propose to use 5 neuropsychological instruments to measure functioning in the following cognitive areas: Attention, processing speed, impulse control, effort, mental flexibility and abstract thinking.

1. Halstead Category Test, Russell Revised Version: The Category Test is an objective test of problem-solving ability, specifically abstract thinking and mental flexibility. The test takes 30-40 minutes to administer. Our previous work has shown that the Category Test is able to differentiate Veterans with GWI from Gulf War Veterans without GWI. The Category Test has acceptable test-retest reliability and has been used as an outcome in cognitive rehabilitation treatments.
2. The Conner's Continuous Performance Test-3 (CPT-3): The CPT-3 is a measure of ability to alternate attention, inhibit impulses and mental flexibility. The CPT-3 is a valid and reliable measure that and this version includes norms for adults with brain disorders as well as attentional disorders. It can and has been used in treatment efficacy trials.

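### The only recurring open question on new health concerns is tied to attended sessions, and the sources outside sessions are not named or compared by arm as harms data

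*Combined protocol and SAP*

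**What the plan says.** **The session question.** In the PST arm (Study Arms, last PST paragraph), "participants will regularly be asked questions about their perception of the sessions, treatment, and if they have any new health concerns". In the Health Education arm, "participants will regularly be asked questions on their perception of the sessions, treatment and if they have any new health concerns". Both sentences place the question within the sessions. PST is a "12 session PST intervention", scheduled weekly with room to adjust. On delivery, the Sessions section says: "A Study Provider from the East Orange VA will provide the sessions via phone with all participants from all VA sites". The plan does not say who asks the question, how it is worded, or how answers are coded.

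**The risk statement.** Risks and Benefits, Risks, item 3, says of the activity component: "Since the activities are personalized, the exact risks are not known". The same item calls behavioral activation a standard treatment component, encourages participants to talk to their primary care provider, and relies on the Study Provider's clinical judgment to limit risk.

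**Sources outside the sessions.** The team will review participants' "medical records and collect information on previous and future medical treatment including physical and mental health treatment, diagnoses and medication". Research staff give the C-SSRS at screening and at the 12th-session visit. Self-reported conditions, medication and health care use are collected with the Demographic Survey & Healthcare Access forms, which the Summary List of Measures and Timeline marks at baseline, 12 and 24 weeks. Primary care providers are told of participation so that they can raise concerns. The PGIC is given at 12 and 24 weeks.

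**Reporting and analysis.** Incident Reporting opens "In the case that any digital recorders, electronic data, or hard copies of any research files and study data are compromised" and deals with data security and privacy. The Data Analysis section names no harms outcome and no comparison of harms by arm.

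**The concern.** PST encourages Veterans to do more, and the plan accepts that the exact risks of this cannot be listed in advance. Any information on harm in this setting would therefore have to come from the trial itself.

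The one instrument that repeatedly and openly asks about new health problems works only while a Veteran attends sessions. Someone who misses sessions is asked less often, and someone who stops them is not asked this question again. If attendance differs between arms, the number of reports will differ even when the true rates are equal. The arm with poorer attendance would then look safer. The Background itself says that earlier trials in this illness, which sought to increase activity, had poor adherence. The person asking, on the natural reading, also knows the arm.

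The planned sources that do not depend on sessions could correct this, but the plan gives none of them that task. Followed as written, the trial would end with an unstructured set of session remarks and no defined harms table by randomised arm.

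**Working it through.** The documents state no harm rate, attendance rate or safety sample size, so there is no figure to reproduce. The check has three parts.

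**1. Which sources depend on sessions, and which are named as harms data**

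| Source | Tied to attended sessions? | Timing | Named as harms data? |
|---|---|---|---|
| Open question on new health concerns | Yes | During sessions | No |
| C-SSRS by research staff | No, but needs the 12th-session visit | Screening, 12th-session visit | No |
| Self-reported conditions, medication, health care use | No | Baseline, 12, 24 weeks | No |
| PGIC | No | 12, 24 weeks | No |
| Primary care provider notices | No | Spontaneous | No |
| Medical record review | No | Prospective, no subset limit stated | No |

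The third column shows that ascertainment of health events does not end with treatment. The last column shows the gap: nothing is designated, defined or analysed as harms data. The week-4 packet (PSI, BRIQ, PHQ-15, WHO-DAS, WAI) has no open new-health-problem item.

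**2. Share of planned follow-up covered by the sessions**

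Twelve weekly sessions cover about 12 weeks. The timeline table labels the last assessment as 24 weeks (6 months), while the text places it 6 months after treatment, about week 12 + 26 = 38.

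- 12/24 = 50%
- 12/38 = 32%

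The session question is therefore open for half or about a third of follow-up at full attendance. The two labels for the last assessment also need reconciling.

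**3. What unequal attendance would do to session reports (illustration only)**

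Assumptions, none from the documents: 150 per arm (the plan says up to 300 in total and gives no allocation ratio); the same true 12-week risk r in both arms; and an event recorded only if it falls in the attended share a of sessions. Then

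observed risk = 1 − (1 − r)^a.

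With r = 0.20:

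- PST, a = 0.6: 1 − 0.8^0.6 = 0.125, about 19 of 150
- Control, a = 0.9: 1 − 0.8^0.9 = 0.182, about 27 of 150
- Ratio: 0.125/0.182 = 0.69

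The chance of a nominally significant difference (two-sided 0.05, normal approximation) uses a difference of 0.0566, a pooled standard error of 0.0416 and an unpooled one of 0.0415: Φ[(0.0566 − 1.96 × 0.0416)/0.0415] = Φ(−0.60), about 27%.

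For r from 5% to 30% and PST attendance from 80% down to 50%, against 90% in control, the ratio runs from 0.90 to 0.56. With 90% in both arms it is 1.0. The model overstates the loss, because an event in a missed week can be reported at a later session.

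**The case against.** A reader might infer that harms are gathered only in sessions and that all ascertainment stops with treatment. The documents do not support this. The C-SSRS at the 12th-session visit, the self-report forms and PGIC at 12 and 24 weeks, the primary care route and the record review all lie outside sessions, and several extend past treatment. Veterans who leave may also attend a paid exit assessment.

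A reader might also infer that a Veteran who stops sessions is lost to the study. The sentence "We will not reach out to Veterans who do not wish to continue in the study" concerns leaving the study, not stopping sessions. The sentence before it promises effort to reach participants for assessments, and the analysis is primarily by intention to treat.

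Nor do the documents show that PST would look safer, or that any particular share of events would be missed. They report no attendance by arm, and event rates after coaching ends need not match those during it. That the provider asks the question is an inference, though a natural one. No aim or hypothesis concerns safety, and the risk item describes precautions.

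These objections stand, and they limit the claim. They do not remove the gap: the other sources exist but none is assigned to harms. The C-SSRS covers suicidality alone and is given once after screening, provider notices are spontaneous, and symptom scales summarise severity rather than record events.

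**Conclusion.** The point holds in a limited form. The only recurring open question on new health concerns depends on attendance and ends with the sessions. The planned sources that do not share this weakness are neither designated as harms data nor compared by arm, and the incident rule concerns compromised data only.

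A harms comparison resting on session reports would be biased if attendance differed between arms. The size cannot be stated from the documents: it is nil with equal attendance, and the ratio of 0.69 above holds only under assumed attendance and risk. The 50% and 32% are shares of follow-up time, not shares of events missed. The conclusion assumes that the provider asks the question and that record review covers all enrolled Veterans, as its unrestricted wording suggests. Whether review continues after withdrawal is not stated.

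This does not threaten the primary disability comparison. It is an inexpensive improvement that should be made, because without it the trial could say little about the comparative safety of telephone PST.

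**What to change.** - **Name the harms data.** State that hospitalisations, emergency visits, injuries, suicide attempts and deaths, from randomisation to last follow-up, are collected for every randomised Veteran, whether or not sessions continue and within the consent given.
- **Name the sources.** Use the planned record review, the Healthcare Access and self-reported conditions forms, and the 12th-session C-SSRS.
- **Separate extraction from delivery.** Have existing staff who do not deliver sessions extract the events, masked to arm where feasible.
- **Add one item.** Put a single new-health-problem question, worded identically in both arms, in the week-4, week-12 and last-follow-up questionnaires.
- **Report.** Add to the Data Analysis section a table of these events by randomised arm, with session reports listed separately.
- **Reconcile the last time point** between the timeline table and the text, so that the window is the same for everyone.

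The cost is protocol wording, one questionnaire item, one extraction form with some staff time, and one table. Care outside the VA would be caught only by self-report, which depends on questionnaires being returned, so the table should show how many Veterans contributed each source by arm.
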